7.2.1.1 Procedures for Participants Exhibiting Serotonin Syndrome (SS)

There is a rare chance that epacadostat could cause an increase in serotonin levels in the brain that might trigger SS [Boyer EW, Shannon M 2005], when administered in combination with other serotonergic agents. This syndrome has been most closely associated with use of MAOIs, meperidine, linezolid, or methylene blue; all of these agents are prohibited during the study.

Selective serotonin reuptake inhibitors (SSRIs) and serotonin/norepinephrine reuptake inhibitors (SNRIs) are permitted in the study. Serotonin syndrome usually manifests with autonomic changes, mental status changes, and neurological findings. These mild, moderate, and severe signs and symptoms of SS (summarized in Table 5) should be evaluated in the context of possible comorbid conditions as well.

The following procedures will be implemented if participant exhibit the signs/symptoms of SS (described in Table 5), including tremor; hyperreflexia; spontaneous, ocular, or inducible clonus; together with agitation, fever, diaphoresis, or muscle rigidity.

- Immediately interrupt study treatment administration.
- Immediately interrupt any SSRI or SNRI administration.
- Provide appropriate medical management of the participant until all signs/symptoms are resolved (eg, IV fluids and/or sympathomimetic amines for hypotension, benzodiazepines for agitation, administration of 5-hydroxytryptamine antagonists such as cyproheptadine).
- If etiologies other than SS are excluded, pembrolizumab administration may be resumed unless other AE management guidelines apply for the specific event.
- If participant chooses to remain in the study, restart study treatment after the SSRI or SNRI has been discontinued, no sooner than after 5 half-lives have elapsed for the specific SSRI or SNRI in question, and after resolution of signs/symptoms of SS. The SSRI or SNRI dosing MAY NOT be restarted.
- If participant chooses to withdraw from the study, or must restart treatment with SSRI or SNRI, the participant should be scheduled for a follow-up visit. Treatment with SSRI or SNRI may be initiated 2 weeks after resolution of signs and symptoms of SS.

- If a participant had experienced moderate or severe unconfounded SS in the opinion of the investigator, without concomitant SSRI or SNRI usage, or serotonergic concomitant medications, only pembrolizumab administration may be resumed; epacadostat/placebo treatment should be permanently discontinued.

Table 5 Signs and Symptoms of Serotonin Syndrome

Seriousness	Autonomic signs	Neurological signs	Mental status	Other
Mild	Afebrile or low-grade fever Tachycardia Mydriasis Diaphoresis or shivering	Intermittent tremor Akathisia Myoclonus Mild hyperreflexia	Restlessness Anxiety	
Moderate	Increased Tachycardia Fever (up to 41° C) Diarrhea with hyperactive bowel sounds Diaphoresis with normal skin color	Hyperreflexia Inducible clonus Ocular clonus (slow continuous lateral eye movements) Myoclonus	Easily startled Increased confusion Agitation and hypervigilance	Rhabdomyolysis Metabolic acidosis Renal Failure Disseminated intravascular coagulopathy (secondary to hyperthermia)
Severe	Temperature often more than 41° C (Secondary to increased tone)	Increased muscle tone (lower limb > upper) Spontaneous clonus Substantial myoclonus or hyperreflexia	Delirium Coma	As above

Source: [Boyer, E. W. 2005]

7.2.1.2 Dose Modification and Toxicity Management of Infusion-reactions Related to Pembrolizumab

Pembrolizumab may cause severe or life threatening infusion-reactions including severe hypersensitivity or anaphylaxis. Signs and symptoms usually develop during or shortly after drug infusion and generally resolve completely within 24 hours of completion of infusion. Dose

modification and toxicity management guidelines on pembrolizumab associated infusion reaction are provided in [Table 6](#).

Table 6 Pembrolizumab Infusion Reaction Dose Modification and Treatment Guidelines

NCI CTCAE Grade	Treatment	Premedication at Subsequent Dosing

Grade 1 Mild reaction; infusion interruption not indicated; intervention not indicated
	
Increase monitoring of vital signs as medically indicated until the participant is deemed medically stable in the opinion of the investigator.
	
None

Grade 2 Requires therapy or infusion interruption but responds promptly to symptomatic treatment (e.g., antihistamines, NSAIDs, narcotics, IV fluids); prophylactic medications indicated for ≤ 24 hrs
	
Stop Infusion. Additional appropriate medical therapy may include but is not limited to: IV fluids Antihistamines NSAIDs Acetaminophen Narcotics
 
Increase monitoring of vital signs as medically indicated until the participant is deemed medically stable in the opinion of the investigator.
 
If symptoms resolve within 1 hour of stopping drug infusion, the infusion may be restarted at 50% of the original infusion rate (e.g. from 100 mL/hr to 50 mL/hr). Otherwise dosing will be held until symptoms resolve and the participant should be premedicated for the next scheduled dose.
 
Participants who develop Grade 2 toxicity despite adequate premedication should be permanently discontinued from further study treatment
	
Participant may be premedicated 1.5 h (\pm 30 minutes) prior to infusion of pembrolizumab with: Diphenhydramine 50 mg po (or equivalent dose of antihistamine). Acetaminophen 500-1000 mg po (or equivalent dose of analgesic).

NCI CTCAE Grade	Treatment	Premedication at Subsequent Dosing

Grades 3 or 4
 
Grade 3: Prolonged (ie, not rapidly responsive to symptomatic medication and/or brief interruption of infusion); recurrence of symptoms following initial improvement; hospitalization indicated for other clinical sequelae (e.g., renal impairment, pulmonary infiltrates)
 
Grade 4: Life-threatening; pressor or ventilatory support indicated
	
Stop Infusion.
 
Additional appropriate medical therapy may include but is not limited to:
 
Epinephrine**
 
IV fluids
 
Antihistamines
 
NSAIDs
 
Acetaminophen
 
Narcotics
 
Oxygen
 
Pressors
 
Corticosteroids
 
Increase monitoring of vital signs as medically indicated until the participant is deemed medically stable in the opinion of the investigator.
 
Hospitalization may be indicated.
 
**In cases of anaphylaxis, epinephrine should be used immediately.
 
Participant is permanently discontinued from further study treatment.
	
No subsequent dosing

Appropriate resuscitation equipment should be available at the bedside and a physician readily available during the period of drug administration. For further information, please refer to the Common Terminology Criteria for Adverse Events v4.0 (CTCAE) at http://ctep.cancer.gov Abbreviations: CTCAE = Common Terminology Criteria for Adverse Events; IV = intravenous; NCI = National Cancer Institute; NSAIDs = nonsteroidal anti-inflammatory drugs; PO = oral.
		

7.2.1.3 Interruptions Unrelated to Adverse Events

Dosing interruptions are permitted for situations other than treatment-related AEs, such as in the case of medical/surgical events or logistical reasons not related to study treatment (eg, elective surgery, unrelated medical events, participant vacation, or holidays). Participants should be placed back on study therapy within 3 weeks of the scheduled interruption, unless otherwise discussed with MSD. The reason for interruption should be documented in the participant's study record.

7.2.2 Second Course Phase (Retreatment)

NOTE: As of Amendment 03, disease assessment will be performed by the investigator per local SoC guidelines; placebo will not be administered after unblinding. This section has been updated accordingly.

All participants who stop study treatment with SD or better may be eligible for up to an additional 17 cycles (approximately 1 year) of combination treatment of pembrolizumab plus epacadostat or pembrolizumab monotherapy, if they progress after stopping study treatment from the initial treatment phase. This retreatment is termed the Second Course Phase of this study and is only available if the study remains open and the participant meets the following conditions:

Either

- Stopped initial treatment with study treatment after attaining CR evaluated by the local investigator based on RECIST 1.1, and
 - Was treated with at least 8 cycles of study treatment before discontinuing treatment, and
 - Received at least 2 treatments with pembrolizumab beyond the date when the initial CR was declared

OR

- Had SD, PR, or CR and stopped study treatment after completion of 35 cycles (approximately 2 years) of study treatment

AND

- Experienced radiographic disease progression verified by Investigator assessment based on RECIST 1.1 after stopping initial treatment, and
 - No new anticancer treatment was administered after the last dose of study treatment, and
 - The participant meets all of the safety parameters listed in the inclusion criteria and none of the safety parameters listed in the exclusion criteria, and
 - The study is ongoing.

Participants who enter the Second Course Phase will be retreated with the same combination, and epacadostat dose level as when they last received the combination of pembrolizumab plus epacadostat or pembrolizumab monotherapy in the initial treatment phase, unless a study-wide decision is otherwise announced by the DMC or Sponsor via an administrative memo. Note: If

epacadostat was discontinued it should not be restarted. Treatment will be administered for up to an additional 17 cycles (approximately 1 year) using the Second Course Phase SoA in Section 2.2.

An objective response or disease progression that occurs during the Second Course Phase for a participant will not be counted as an event for the primary analysis in this study.

7.3 Method of Treatment Assignment

Treatment allocation/randomization will occur centrally using an interactive voice response system / integrated web response system (IVRS/IWRS). There are 2 study treatment arms. Participants will be assigned randomly in a 1:1 ratio to pembrolizumab + epacadostat or pembrolizumab + matching placebo.

7.3.1 Stratification

Treatment allocation/randomization will be stratified according to the following factors:

1. Bellmunt risk score of 0 vs 1 vs ≥ 2 .

The Bellmunt risk score for each participant is calculated by the presence of the total number of the following risk factors (each counts a score of 1) at baseline:

- ECOG PS ≥ 1
 - Presence of liver metastases
 - Hemoglobin level < 10 g/dL
 - Time from last chemotherapy dose (< 3 months [Note: 90 days will be used] from randomization)
2. PD-L1 expression from tumor tissue samples, based on CPS ≥ 10 vs CPS < 10 per IHC assay, as assessed by the designated central laboratory

7.4 Blinding

The study is double-blinded using epacadostat and matching placebo, such that the participant, the study site personnel, and the Sponsor and MSD or designee do not know the identity of the treatment arm.

Note: As of Amendment 03, the study will be unblinded after the last participant completes the Week 9 imaging assessment for efficacy analysis. After unblinding, for participants who are benefiting from study treatment and continue study treatment after discussion with the investigator, the participant, study site personnel, Sponsor and MSD or designee will be informed of the study treatment they receive (eg, pembrolizumab or pembrolizumab in combination with epacadostat).

Pembrolizumab, which will be dosed to all participants in both treatment arms, will not be blinded.

See Section 9.1.11 for a description of the method of unblinding a participant during the trial, should such action be warranted.

7.5 Preparation/Handling/Storage/Accountability

7.5.1 Dose Preparation

Details on preparation and administration of IV pembrolizumab are provided in the Pharmacy Manual. Epacadostat and matching placebo are oral tablets and do not require preparation.

For epacadostat in such cases where a participant is unable to swallow tablets or has a feeding tube instruction for dose crushing, administration and dose preparation are detailed in the Pharmacy Manual. In addition written guidance for safe handling of the epacadostat tablets will be provided to the participant/caregivers.

7.5.2 Handling, Storage and Accountability

The investigator or designee must confirm appropriate temperature conditions have been maintained during transit for all study treatment received and any discrepancies are reported and resolved before use of the study treatment.

Only participants enrolled in the study may receive study treatment and only authorized site staff may supply or administer study treatment. All study treatments must be stored in a secure, environmentally controlled, and monitored (manual or automated) area in accordance with the labeled storage conditions with access limited to the investigator and authorized site staff.

The investigator, institution, or the head of the medical institution (where applicable) is responsible for study treatment accountability, reconciliation, and record maintenance (ie, receipt, reconciliation, and final disposition records).

For all trial sites, the local country MSD personnel or designee will provide appropriate documentation that must be completed for drug accountability and return, or local discard and destruction if appropriate. Where local discard and destruction is appropriate, the investigator is responsible for ensuring that a local discard/destruction procedure is documented.

The trial site is responsible for recording the lot number, manufacturer, and expiry date for any locally purchased product as per local guidelines unless otherwise instructed by MSD.

The investigator shall take responsibility for and shall take all steps to maintain appropriate records and ensure appropriate supply, storage, handling, distribution and usage of study treatments in accordance with the protocol and any applicable laws and regulations.

7.6 Treatment Compliance

Interruptions from the protocol-specified treatment plan for greater than 12 weeks from the last dose require consultation between the Investigator and MSD and written documentation of the collaborative decision on participant management.

7.6.1 Administration and Compliance of Pembrolizumab

Administration of pembrolizumab will be witnessed by the investigator and/or trial staff. The total volume of trial medication infused will be compared with the total volume prepared to determine compliance with each dose administered.

Pembrolizumab will be administered on an out-patient basis. Instructions for preparing and administering pembrolizumab are provided in the Pharmacy Manual.

7.6.2 Administration and Compliance of Epacadostat or Matching Placebo

Participants will take their dose of epacadostat or matching placebo in the morning and evening, approximately 12 hours apart without regard to food. If the morning or evening dose is missed by more than 4 hours, that dose should be skipped and the next scheduled dose should be taken at the usual time. If the participant vomits after taking a tablet, the dose should not be re-administered until the next scheduled dose. Participants will self-administer epacadostat or matching placebo except on Cycle 1 Day 1 (C1D1), and Cycle 2 Day 1 (C2D1), when the morning dose will be given at the study site clinic prior to the pembrolizumab infusion.

Participants will be instructed to bring all study treatments with them to the study visits in order for site personnel to conduct tablet counts to assess study treatment accountability. Investigators and their staff should evaluate compliance at each visit, and take appropriate steps to optimize compliance.

7.7 Concomitant Therapy

7.7.1 Acceptable Concomitant Medications

All treatments that the investigator considers necessary for a participant's welfare may be administered or changed at the discretion of the investigator in keeping with the community standards of medical care and prohibited medications in this study. All concomitant medication will be recorded on the case report form (CRF) including all prescription, over-the-counter, herbal supplements, and IV medications and fluids. If changes occur during the study period, documentation of drug dosage frequency, route, and date will also be included on the CRF.

Palliative and supportive care is permitted during the course of the study for underlying medical conditions and management of symptoms. Surgery for tumor control is not permitted during the study. Palliative radiotherapy is permitted to a limited number of lesions if considered medically necessary by the treating physician as long as the lesions are NOT a RECIST 1.1-defined target lesion. Study treatment should be held during the course of palliative radiotherapy and should be resumed no earlier than the next scheduled administration of study treatment. The specifics of the radiation treatment, including the location, will be recorded.

All concomitant medications received within 28 days before the first dose of study treatment through the Safety Follow-up Visit should be recorded. After the Safety Follow-up Visit, record all medications taken for SAEs and ECIs as defined in Section 9.3. If a participant enters into second course therapy, all concomitant medications received within 30 days before the first dose of second course treatment should be recorded. Following second course therapy Safety Follow-up Visit, record all medications taken for SAEs and ECIs as defined in Section 9.3.

7.7.2 Prohibited Concomitant Medications

Medications or vaccinations specifically prohibited in the exclusion criteria are not allowed during the ongoing study. If there is a clinical indication for any medication or vaccination specifically prohibited, discontinuation from trial therapy or vaccination may be required. The investigator should discuss any questions regarding this with the MSD Clinical Director. The

final decision on any supportive therapy or vaccination rests with the investigator and/or the participant's primary physician. However, the decision to continue the participant on study treatment requires the mutual agreement of the investigator, MSD, and the participant.

If a study participant must receive a medication prohibited for concomitant use with epacadostat during the study treatment period, treatment with epacadostat (or placebo) must be interrupted or discontinued. Examples of such medications include MAO inhibitors, and UGT1A9 inhibitors. Participants may continue on treatment with pembrolizumab after consultation with MSD.

Listed below are specific restrictions for concomitant therapy or vaccination:

Participants are **prohibited** from receiving the following therapies during the Screening, Treatment, and Second Course Phases of this study:

1. Investigational agents other than pembrolizumab and epacadostat.
2. Any anti-cancer medications, including chemotherapy or biologic therapy other than the study treatments.
3. Immunotherapy not specified in this protocol.
4. Prolonged therapy with systemic glucocorticoids (>7 days) for any purpose other than to modulate symptoms from an AE, SAE, or ECI or for use as a pre-medication for chemotherapy or in participants with a known history of an IV contrast allergy administered as part of CT radiography. Brief, limited use of systemic corticosteroids (≤ 7 days) are permitted where such use is considered SOC (eg, for COPD exacerbation).

Replacement doses of steroids (for example, prednisone 5 to 7.5 mg daily) are permitted while on study, as is the use of local steroids.

5. Radiation therapy or surgery:

Note: Radiation therapy or surgery to a symptomatic solitary lesion is allowed. No pembrolizumab infusions are permitted during radiation therapy or procedure and epacadostat or matching placebo should be stopped the day treatment begins. Study treatment may be resumed as early as 1 week after treatment if the participant's symptoms are improving and not requiring corticosteroids for management. MSD consultation is required for study treatment restart after radiation therapy or surgery. If study treatment is not resumed within 12 weeks of completing treatment (radiation therapy or surgery), the participant should discontinue study treatment permanently.

6. Live attenuated vaccine within 30 days before the first dose of study treatment and while participating in the study.
 - Examples of live vaccines include, but are not limited to, the following: measles, mumps, rubella, chicken pox, yellow fever, rabies, BCG, and typhoid vaccine. Seasonal influenza vaccines for injection are generally killed virus vaccines and are allowed; however, intranasal influenza vaccines are live attenuated vaccines and are not allowed.
7. Any MAOI or drug associated with significant MAO inhibitory activity agents is prohibited from 21 days before starting study treatment through 2 weeks after the final dose of epacadostat or matching placebo has been taken.

- Including, but not limited to, hydrazines (example phenelzine), meperidine, caroxazone, linezolid, echinopsidine, methylene blue, furazolidon, tranlycypromine, brofaromine, metralindole, minaprine, moclobemide, pirlindole, toloxatone, lazbemide, pargyline, rasagiline, selegiline.
8. Any UGT1A9 inhibitor, including: acitretin, amitriptyline, androsterone, cyclosporine, dasatinib, diclofenac, diflunisal, efavirenz, erlotinib, flutamide, gefitinib, gemfibrozil, glycyrrhetic acid, glycyrrhizin, imatinib, imipramine, ketoconazole, linoleic acid supplements, mycophenolic acid, niflumic acid, nilotinib, phenobarbital, phenylbutazone, phenytoin, probenecid, quinidine, ritonavir, sorafenib, sulfapyrazone, valproic acid, and verapamil.

Note: Ketoconazole 2% topical cream is allowed.

Participants who, in the assessment of the Investigator, require the use of any of the aforementioned treatments for clinical management should be removed from the trial.

All treatments that the Investigator considers necessary for a participant's welfare may be administered at the discretion of the Investigator in keeping with the community standards of medical care. All concomitant medication will be recorded on the electronic case report form (eCRF) including all prescription, over-the-counter (OTC) products, herbal supplements, and IV medications and fluids. If changes occur during the trial period, documentation of drug dosage, frequency, route, and date should also be included on the eCRF.

All concomitant medications received within 28 days prior to the first dose of trial treatment and up to 30 days after the last dose of trial treatment should be recorded. Concomitant medications administered 30 days after the last dose of trial treatment should be recorded for SAEs and events of clinical interest (ECIs) as defined in Section 9.3.7

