8.1 Discontinuation of Study Treatment

Discontinuation of study treatment does not represent withdrawal from the study.

As certain data on clinical events beyond study treatment discontinuation may be important to the study, they must be collected through the participant's last scheduled follow-up, even if the participant has discontinued study treatment. Therefore, all participants who discontinue study treatment prior to completion of the protocol-specified treatment period will still continue to participate in the study as specified in Section 2 - SoA and Section 9.9.5 – Discontinued Participants Continuing to be Monitored in the Study.

Participants may discontinue study treatment at any time for any reason or be dropped from the study treatment at the discretion of the investigator should any untoward effect occur. In addition, a participant may be discontinued from study treatment by the investigator or MSD if study treatment is inappropriate, the trial plan is violated, or for administrative and/or other

safety reasons. Specific details regarding procedures to be performed at study treatment discontinuation are provided in Section 9.1.10 Withdrawal/Discontinuation.

A participant must be discontinued from study treatment but continue to be monitored in the study for any of the following reasons:

- The participant or participant's legally acceptable representative requests to discontinue study treatment.
- The participant has a medical condition or personal circumstance which, in the opinion of the Investigator and/or MSD, placed the participant at unnecessary risk from continued administration of study treatment.
- The participant has a confirmed positive serum pregnancy test.
- Participant chooses to discontinue study treatment and remains in the study to be followed for progression and survival.
- Participant has received 35 cycles (approximately 2 years) of treatment with pembrolizumab.
- The study is terminated by the sponsor.
- The study is terminated by the local health authority, IRB, or IEC.
- Any progression or recurrence of any malignancy, or any occurrence of another malignancy that requires active treatment.

Note: Surgical excision of non-urothelial cancer is allowed. Refer to Section 7.7 – Concomitant Therapy for radiation and surgery allowed for urothelial cancer.

- The occurrence of unacceptable adverse experiences not caused by an underlying malignancy as described in Section 7.2.1.

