8.2 Withdrawal from the Study

A participant must be withdrawn from the study if the participant or participant's legally acceptable representative withdraws consent from the study.

If a participant withdraws from the study, they will no longer receive study treatment or be followed at scheduled protocol visits.

Specific details regarding procedures to be performed at the time of withdrawal from the study are outlined in Section 9.1.10 – Withdrawal/Discontinuation. The procedures to be performed should a participant repeatedly fail to return for scheduled visits and/or if the study site is unable to contact the participant are outlined in Section 8.3.

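### Section 7.7.2 lets a participant who needs an MAO or UGT1A9 inhibitor stay on pembrolizumab and also tells sites to remove that participant from the trial, so whether the Week 9 scan is obtained can depend on the site.

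*Combined protocol and SAP*

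**What the plan says.** All of the text below is current; none of it is in the amendment summary or marked as no longer applicable.

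- **Section 7.7.2, opening paragraphs.** For any prohibited medication, "the decision to continue the participant on study treatment requires the mutual agreement of the investigator, MSD, and the participant". If the medication is prohibited specifically with epacadostat, the tablet (active or placebo) must be interrupted or stopped. The section adds: "Examples of such medications include MAO inhibitors, and UGT1A9 inhibitors". It then says: "Participants may continue on treatment with pembrolizumab after consultation with MSD".
- **Section 7.7.2, numbered list.** Item 7 covers MAO inhibitors and item 8 UGT1A9 inhibitors, the same two classes. After the list, participants who in the investigator's assessment "require the use of any of the aforementioned treatments for clinical management should be removed from the trial".
- **Section 8.1.** "Discontinuation of study treatment does not represent withdrawal from the study".
- **Section 8.2.** "A participant must be withdrawn from the study if the participant or participant's legally acceptable representative withdraws consent from the study". This is the one mandatory ground given there. A withdrawn participant has no further scheduled visits.
- **Section 9.2.1.2.** The on-study scan is due 63 days (±7) after randomisation, and no later imaging is mandated.
- **Section 9.2.1.3.** A participant who stops study treatment before Week 9 is scanned at discontinuation (±4 weeks), unless imaged in the preceding 4 weeks.
- **Sections 10.5.1 and 10.6.1.1.** The primary endpoint is ORR in all randomised participants, estimated by arm with a 95% Clopper-Pearson interval.

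**The concern.** The same event, a new clinical need for an item 7 or item 8 drug, leads to two different outcomes. Under the opening paragraphs the participant remains on pembrolizumab, keeps attending visits and reaches the Week 9 scan. Under the closing sentence the participant is taken out of the trial. If a site reads that as withdrawal, Section 8.2 ends scheduled visits and the Week 9 scan is not done.

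The intention-to-treat (ITT) denominator keeps everyone randomised, but whether a response can be observed in such a participant would depend on which sentence the site follows. With about 42 participants per arm and one scheduled on-study read, avoidable losses of this kind are worth preventing.

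**Working it through.** **1. Do the two instructions cover the same participants?**

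| Step | Opening paragraphs of 7.7.2 | Closing sentence of 7.7.2 |
|---|---|---|
| Trigger | Needs a drug prohibited with epacadostat; MAO and UGT1A9 inhibitors named | Needs any treatment listed above; items 7 and 8 are these classes |
| Tablet | Interrupted or stopped | Ends with removal |
| Pembrolizumab | May continue after consultation | Ends with removal |
| Place in the study | Remains | Removed from the trial |

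The triggers overlap completely for items 7 and 8, and the last two rows cannot both hold. Three readings of the closing sentence are possible:

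- *Withdrawal from the study*: conflicts with continued pembrolizumab.
- *Stopping all study treatment*: conflicts with continued pembrolizumab.
- *Stopping the tablet only*: consistent with the opening paragraphs, but the sentence does not say so, and it also covers list items unrelated to the tablet.

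**2. The plan's own figures.** Inputs from Section 10.9: n = 42 per arm and 9 to 12 responders. The Clopper-Pearson limits are the 2.5% quantile of Beta(x, n−x+1) and the 97.5% quantile of Beta(x+1, n−x).

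| Responders | ORR | Recomputed 95% CI | Table 12 |
|---|---|---|---|
| 9 | 21.4% | 10.3 to 36.8 | 10.3 to 36.8 |
| 10 | 23.8% | 12.1 to 39.5 | 12.0 to 39.4 |
| 11 | 26.2% | 13.9 to 42.0 | 13.9 to 42.0 |
| 12 | 28.6% | 15.7 to 44.6 | 15.7 to 44.6 |

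The table reproduces. The 0.1-point differences in the second row are rounding (unrounded limits 12.05 and 39.45).

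**3. Size of one case.** 1/42 = 2.4 points of one arm's ORR. This is a maximum: it needs the participant to be a responder who has no usable scan.

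**4. Several cases.** The documents give no frequency, so the number removed per arm before Week 9, m, is assumed to be 1 to 4. The calculation takes a true rate of 9/42 = 21.4%, response unrelated to removal, and no scan in anyone removed. Expected responders lost = m × 9/42, and the ORR shift is that number divided by 42.

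| m | Expected responders lost | Expected shift | Maximum shift (m/42) |
|---|---|---|---|
| 1 | 0.21 | 0.5 points | 2.4 points |
| 2 | 0.43 | 1.0 points | 4.8 points |
| 4 | 0.86 | 2.0 points | 9.5 points |

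For comparison, the Table 12 interval at 9 responders is 26.5 points wide. A fall from 9/42 to 7/42 (16.7%, 7.0 to 31.4) needs two removals in one arm, both would-be responders and both unscanned. For two given participants, the chance that both are responders is 0.214² = 4.6% if independent.

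**5. Does the discontinuation scan close the gap?** Partly. It is waived if imaging was done in the previous 4 weeks, and baseline imaging may be up to 28 days old at randomisation. For example, with a baseline scan 7 days before randomisation and a stop 14 days after, the gap is 21 days. The waiver then applies and no post-baseline scan is required. Section 9.2.1.3 is also written for stopping study treatment and does not mention removal from the trial.

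**The case against.** The strongest reply is that this is a small wording conflict with safeguards around it. Much of that stands.

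- **Other contradictions.** A reader might infer that no reading satisfies all of Section 7.7.2 together with 8.1. That goes too far. The item 5 note, "Radiation therapy or surgery to a symptomatic solitary lesion is allowed", with "Study treatment may be resumed as early as 1 week after treatment if the participant's symptoms are improving", is an express exception. Section 8.1 separates stopping treatment from leaving the study, but does not itself forbid a removal rule. The direct clash is on items 7 and 8.
- **Force of the wording.** The closing sentence says should, not must, and a site might take it to mean removal from trial therapy. That softens the instruction but leaves it unclear, and removal from all trial therapy would still contradict continued pembrolizumab.
- **Loss of data.** A reader might infer that a removed participant has no efficacy read and drops out of safety follow-up. Section 9.1.10 asks for final-visit activities at discontinuation or withdrawal, Section 9.2.1.3 for a discontinuation scan, and Section 9.3.1 for adverse event reporting to 90 days (30 days if new anticancer therapy starts). The loss is partial.
- **Counting as a non-responder.** This is the natural consequence of an all-randomised denominator, but Sections 10.4 to 10.6 state no rule for a participant without a post-baseline scan.
- **Frequency.** Item 8 includes familiar drugs such as diclofenac and verapamil, which might suggest frequent cases. Exclusion criterion 21 bars recent users and anyone expected to need an item 7 or 8 drug, so only unforeseen needs over about nine weeks remain.
- **Between-arm bias.** None is shown. The rule applies to active tablet and placebo alike while the study is blinded, and no hypothesis is tested.

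**Conclusion.** The contradiction is real and affects conduct. For item 7 and item 8 drugs, one sentence keeps the participant on pembrolizumab and in the study, and another removes the participant. A site following the second can lose the Week 9 scan in someone who would otherwise have had it.

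The numerical effect is likely to be small. On the assumed 1 to 4 removals per arm, the expected shift is 0.5 to 2.0 points, even with every case removed and no discontinuation scan. This rests on a 21.4% response rate, on response being unrelated to removal, and on a frequency the documents do not give. The documents do not support a claim that the primary result is biased towards either arm, or that safety follow-up is lost. The case for acting is that the loss is avoidable and the correction is cheap.

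**What to change.** 1. Reconcile the opening paragraphs and the closing sentence of Section 7.7.2 into one study-treatment rule for item 7 and item 8 drugs. Which rule applies is for the sponsor to decide.
2. Replace the removal wording with wording that affects study treatment only, and state that a randomised participant stays in the study unless consent is withdrawn.
3. State the imaging consequence. Those still on any study treatment have the Week 9 scan. Those who stop all study treatment before Week 9 have the discontinuation scan under Section 9.2.1.3 and the Safety Follow-up Visit.
4. If the sponsor also wants a Week 9 scan after full discontinuation, three other places must be aligned: the Section 2.1 schedule, which sends discontinuers straight to end of treatment and Safety Follow-up; Section 5.1, which ends participation after Safety Follow-up; and Section 9.2.1.3. Adding the scan in 7.7.2 alone would create a new conflict.

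The cost is protocol wording, plus scans and follow-up in a few participants who are off one or both drugs.
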